Topical analgesic have a place in managing musculoskeletal pain but their scientific efficacy has usually been anecdotal and seldom subjected to investigational scrutiny. These topical agents are relatively safe but may still have adverse effects by virtue of their pharmacological compositions. The use of natural compounds e.g. essential oils from selective herbal extracts have been used by many persons from tropical and subtropical regions for medicinal purposes including pain.

Thus, the objective of this study is to evaluate the efficacy and onset of action of Bonipar, a topical analgesic derived from a variety of essential oils, in controlling pain in patients with acute and chronic musculoskeletal pain, as compared to the topical NSAID, Diclofenac topical solution 1.5%.

Design & Procedures

- Describe the study, providing detail regarding the study intervention (drug, device, physical procedures, manipulation of the subject or the subject's environment, etc.). Discuss justifications for placebo control, discontinuation or delay of standard therapies, and washout periods if applicable. Identify procedures, tests and interventions performed exclusively for research purposes or more frequently than standard of care. Include alternative therapies, concurrent therapies discontinued per protocol, risk benefit ratio, and use of tissue/specimens. Discuss monitoring during washout periods if applicable. Include brief description of follow-up, if any.

This study is a non-inferiority study comparing efficacy and onset of action between the herbal extracts topical solution, Bonipar, and diclofenac sodium topical solution, diclofenac topical solution 1.5% (approved by the FDA as a topical analgesic). Approximately 240 Duke patients will be recruited from Duke Pain Clinic, and selected Duke primary care practices, as well as the Durham VA site. Individuals who report acute (less than 3 months duration) or chronic musculoskeletal pain of any intensity will be considered for enrollment into the study. After obtaining consent, eligible subjects will be will be randomized to receive Bonipar or diclofenac topical solution 1.5%.

For study purposes, diclofenac topical solution 1.5% will be used off-label—that is, it may be used for pain not known to be caused by osteoarthritis. However, this study does not aim to identify a new indication for diclofenac topical solution 1.5%.

Baseline Assessments

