All subjects will be instructed on the application of the assigned drug. Subjects will be asked to apply the study drug 2 pumps 2 times a day to be applied topically on the affected area during a one week treatment period. Application instructions will be provided to the subjects. Prior to the first use, the study coordinator will prime the pump by pushing down fully 4 times, and to discard any solution to ensure an accurate dose is delivered during first use.

Study Drug Application at Home

Written study drug application instructions, storage instructions, and a study diary will be provided to all subjects at the time of discharge from the clinic.

At home, subjects will continue to apply the study drug twice a day. In the 1 week diary, subjects will record daily drug application, pain scores before and after application and any other oral pain medication taken. Subjects are permitted in the study to take acetaminophen (325 to 650 mg tablet up to 4 times a day) if pain persists even with the study drug application.

Subjects will be instructed to observe the following instructions:

1. Please wash and dry hands before and after use.
2. Do not apply to skin with open wounds, or blistered or inflamed areas of the skin.
3. Avoid contact with your eyes and mucous membranes.
4. Do not apply external heat.
5. Do not shower for at least 30 minutes after applying study drug.

6. Do not wear clothing over the treated area until the area is dry.
7. Do not take other NSAID (like aspirin, ibuprofen, naproxen, ketorolac, diclofenac, etc.) while enrolled on this study. Please contact the study doctor or research staff if you are unsure.
8. Keep the bottle away from direct sunlight.
9. Protect the treated area from natural or artificial sunlight.
10. Wait until the treated area is dry before applying sunscreen, insect repellent, lotion, moisturizer or cosmetics to the same area.
11. Avoid skin-to-skin contact between other people and the treated area until the treated area is completely dry.

Follow- Up

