- Describe and justify any costs that the subject will incur as a result of participation; ordinarily, subjects should not be expected to pay for research without receiving direct benefit.

There will be no additional costs as a result of being in this study. Bonipar and diclofenac topical solution 1.5% will be provided free of charge for use in this study.

Data Analysis & Statistical Considerations

- Describe endpoints and power calculations. Provide a detailed description of how study data will be analyzed, including statistical methods used, and how ineligible subjects will be handled and which subjects will be included for analysis. Include planned sample size justification. Provide estimated time to target accrual and accrual rate. Describe interim analysis including plans to stop accrual during monitoring. Phase I studies, include dose escalation schema and criteria for dose escalation with definition of MTD and DLT.

The primary objective of the study is to evaluate the reduction in acute and chronic musculoskeletal pain by Bonipar in comparison to conventional treatment of diclofenac topical solution 1.5%. Pain responses at base line and at two-week follow up will be measured in the scale of 0 to 10, where 0 indicates no pain and 10 indicates highest level of pain. For each patient, primary outcome variable will be measured in two ways: i) compute whether the decrease in pain by 50% between baseline and 1-week follow-up (i.e. binary variable) and, ii) calculate the absolute difference in pain score between baseline and 1-week follow-up (continuous variable). Statistical power and sample size was determined based on the binary outcome variable.

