Initial data characteristics will be compared between groups using chi-square for categorical variables and t-test or Wilcoxon rank sum test for continuous variables. Change in pain from baseline will be compared between two treatment groups using chi-square test for binary variable and t-test or equivalent non-parametric test for continuous variable, as appropriate. The significance level of the test will be targeted at $\alpha=0.05$ (one sided). Non-inferiority will be established, at the 0.05 significance level if the lower limit of equivalent two-sided 90% confidence interval for the difference in success rate is above non-inferiority margin. Multivariable linear regression analysis will be performed to examine the changes in pain score adjusting potential confounders such as type of pain (lumbar vs. other), prior duration with pain. Reports of side effects will also be investigated between two groups. As an exploratory analysis we will evaluate the time to onset of action between two topical drugs, where time to onset variable will be measured within 1 hour (as \leq 15 min, \leq 30 min, \leq 45 min or \leq 60 min) after the application of drugs at clinic. No adjustments will be made for the multiple endpoints testing. All analyses will be conducted using SAS version 9.4.

Analysis will be performed for the full datasets and by pain group (acute and chronic).

Power Calculation:

Preliminary data to base on power analysis

Meta-analysis from Massey et al (Cochrane Database Syst Rev.; (6) 2014) presented data from combined three studies comparing topical diclofenac versus placebo (Joussellin 2003; Predel 2004; Rowbotham 2003). A total of 319 participants were treated with topical diclofenac, and 307 with placebo. The success rate (i.e. patient reported pain relief at least 50%) was 52% (166/319, range 39% to 92%) for group treated with diclofenac and 25% (77/307, range 8% to 36%) for placebo group.

Assumptions behind power calculations:

There will be two equal-sized treatment arms, one containing diclofenac topical solution 1.5% treated patients and the other Bonipar treated patients. The arms will be compared for a difference in success rate (i.e. pain reduction at least 50% from baseline to follow-up at 1 weeks) with Z-test (one-sided at alpha=0.05) using PASS software. Two scenarios will be considered, as follows:

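### Acetaminophen use is allowed and recorded, but no analysis takes it into account, so a patient who reaches 50% relief with its help counts as a study-drug success

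*Combined protocol and SAP*

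**What the plan says.** Under Study Drug Application at Home: "Subjects are permitted in the study to take acetaminophen (325 to 650 mg tablet up to 4 times a day) if pain persists" despite the study drug. This applies to both arms. The same section says that in the diary "subjects will record daily drug application, pain scores before and after application and any other oral pain medication taken".

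Under Data Analysis & Statistical Considerations, the primary outcome has two forms. The binary form, on which the sample size rests, is to "compute whether the decrease in pain by 50% between baseline and 1-week follow-up (i.e. binary variable"). The continuous form is to "calculate the absolute difference in pain score between baseline and 1-week follow-up (continuous variable"). Neither carries a condition on other pain medication.

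The rest of that section does not mention acetaminophen. It has no rule for patients who took it, no rule on scores recorded soon after a dose, no comparison of use between arms and no sensitivity analysis. The regression is of the change score, "adjusting potential confounders such as type of pain (lumbar vs. other), prior duration with pain". The section does not say that pain is meant to be compared regardless of other medication taken.

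**The concern.** The trial's stated objective is the efficacy of Bonipar compared with topical diclofenac. A patient whose pain persists on the assigned product, who takes acetaminophen, and whose 1-week score is then half the baseline score, is counted as a success of the assigned product.

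This matters more than usual because "This study is a non-inferiority study comparing efficacy and onset of action". In a superiority trial, a pull towards no difference works against the sponsor's claim. Here, if Bonipar is the weaker product, it works in favour of the claim. The trigger for acetaminophen is persisting pain, so the weaker arm has more patients who qualify. Acetaminophen need not act differently in the two arms for the difference to shrink.

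**Working it through.** **Inputs from the documents (Power Calculation; Data Analysis & Statistical Considerations).** Diclofenac success 52%; Bonipar 62% under the first planning scenario; margin −10 points; test "with Z-test (one-sided at alpha=0.05) using PASS software"; non-inferiority declared if the lower limit of the two-sided 90% confidence interval lies above −10 points; 76 completers per arm.

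**Input not in the documents.** q, the share of patients failing on study drug alone who reach 50% relief with acetaminophen. Assumed range: 10% to 30%.

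**The plan's own figure.** With unpooled variance, n = (1.645 + 0.842)² × (0.52×0.48 + 0.62×0.38) / (0.10 + 0.10)², which gives 75 per arm. The pooled-variance Z-test gives 76, as stated. Power at 76 is 80.5% unpooled, 80.2% pooled, and 80.0% by exact binomial enumeration of the confidence-interval rule. The stated sample size is sound; the issue is what counts as a success.

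**Effect of acetaminophen on the observed rates.** In each arm, observed rate = p + q(1 − p). With the same q in both arms, observed difference = (1 − q) × true difference.

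**Chance of declaring non-inferiority.** Φ[(difference + 0.10)/SE − 1.645], where SE = √[(p_B(1 − p_B) + p_D(1 − p_D))/76]; B is Bonipar and D is diclofenac.

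Worked case: true rates at the margin (42% v 52%), q = 20%.
- Bonipar: 0.42 + 0.20×0.58 = 0.536
- Diclofenac: 0.52 + 0.20×0.48 = 0.616
- Difference −0.080; SE = √[(0.2487 + 0.2365)/76] = 0.0799
- Φ(0.020/0.0799 − 1.645) = Φ(−1.395) = 8.2%

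Bonipar truly at the margin (42% v 52%):

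| q | Observed rates | Difference | False non-inferiority | Exact binomial |
|---|---|---|---|---|
| 0 | 42.0 v 52.0 | −10.0 | 5.0% | 5.0% |
| 10% | 47.8 v 56.8 | −9.0 | 6.4% | 6.4% |
| 20% | 53.6 v 61.6 | −8.0 | 8.2% | 7.9% |
| 30% | 59.4 v 66.4 | −7.0 | 10.4% | 10.0% |

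Bonipar truly better (62% v 52%):

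| q | Observed rates | Difference | Power |
|---|---|---|---|
| 0 | 62.0 v 52.0 | +10.0 | 80% |
| 20% | 69.6 v 61.6 | +8.0 | 76% |
| 30% | 73.4 v 66.4 | +7.0 | 74% |

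**Cost of counting users as non-successes.** Suppose a share f of the planned successes in each arm used acetaminophen (assumed). The rates become 0.52(1 − f) and 0.62(1 − f).

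| f | Rates (Bonipar v diclofenac) | Power at 76 per arm | n per arm for 80% (unpooled) |
|---|---|---|---|
| 0 | 62.0 v 52.0 | 80% | 75 |
| 10% | 55.8 v 46.8 | 76% | 85 |
| 20% | 49.6 v 41.6 | 72% | 95 |
| 30% | 43.4 v 36.4 | 69% | 103 |

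**The case against.** **The score-only outcome may be deliberate.** Comparing pain at 1 week whatever else was taken is a legitimate question. But the plan does not say that this is the question, and it would still need a supporting analysis, because this definition can mask inferiority.

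**Counting users as failures is not free of bias either.** This stands. If a share f of genuine successes in each arm is reclassified because of incidental use, the true difference shrinks to (1 − f) of itself. At the margin with f = 20%, the rates are 33.6% v 41.6%, the difference is −8.0 points and false non-inferiority is again 8.2%; with f = 30% it is 10.6%. This is why the stricter definition should stand beside the score-only outcome and not replace it.

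**Opioid users.** Inclusion criterion 5 admits patients taking opioids for their pain, and nothing requires opioids to stop. A rule that fails anyone with any oral analgesic recorded would fail a stable opioid user automatically, whatever the change in pain. This also stands and limits the fix.

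**The regression could adjust for use.** The covariate list is open-ended. But acetaminophen use arises after randomisation, and the regression does not address the binary outcome.

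**The effect may be small.** Under Follow-Up, patients without adequate relief may drop out instead, so q could be low. The documents cannot settle this.

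**A larger figure is tempting.** A reader might infer a far higher false rate by assuming that failures convert more often in the weaker arm. With 25% conversion in the Bonipar arm and 15% in the diclofenac arm, the difference is −2.7 points and the false rate about 23%. The documents give no reason for that gap. The larger number of failures in the weaker arm is already in the equal-q formula. Reversing the two percentages gives −13.3 points and a false rate of 2.0%.

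**Conclusion.** The gap is certain; its size is not. Acetaminophen is permitted, recorded, and absent from the outcome definition and every planned analysis. With equal conversion of 10% to 30% of failures, false non-inferiority at the margin rises from 5.0% to between 6.4% and 10.4%. This rests on the assumed q and on conversion being similar in the two arms.

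A reader might infer that the bias always favours non-inferiority. It does so only if Bonipar is truly worse. Under the plan's own 62% v 52% scenario the same dilution works against the sponsor, lowering power to about 76% or 74% at q = 20% or 30%. The direction could also change if conversion were concentrated in the better arm. Nor do the documents support replacing the primary definition outright, which is a choice about the question being asked and costs power. They do support asking that the handling be pre-specified.

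**What to change.** Change the analysis section only; the medication rule stays as it is.

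1. Keep the score-only binary outcome and state explicitly that it ignores other pain medication.
2. Add a key supporting non-inferiority analysis of the binary outcome, with the same margin and confidence-interval rule. Patients with acetaminophen or a newly added oral analgesic recorded on the diary day of the 1-week score, or the day before, count as non-successes. Stable background opioid use does not count as failure.
3. Report acetaminophen use by arm.
4. Conclude non-inferiority only if the score-only and supporting analyses agree.

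The window is set in diary days because the protocol describes daily recording and does not say that clock times are captured. Two practical points follow. The visit may fall a day after the diary week ends (± 1 day), so recent use should then be asked at the visit. Separating new from background medication needs a list of pain medication at entry, which Baseline Assessments does not name.

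The cost is mainly wording, plus reduced power under the stricter definition: about 76%, 72% and 69% at 76 per arm if 10%, 20% and 30% of planned successes used acetaminophen. Because both analyses must agree, power for the overall conclusion cannot exceed the lower of the two. The plan should state this and restate the 52% planning rate for the supporting analysis.

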11. Subjects who, within the past 3 months, have history of heart attack, stroke, or blood clot
12. Recent coronary artery bypass graft surgery (CABG) (i.e., within 6 months of screening)
13. Subject with history of alcohol or drug abuse within the past 3 months
14. Subject with history of severe liver or kidney disease or any other medical condition within 3 months of screening that may interfere with the subject's ability to participate in the study as determined by the Investigator

Subject Recruitment and Compensation

- Describe recruitment procedures, including who will introduce the study to potential subjects. Describe how you will ensure that subject selection is equitable and all relevant demographic groups have access to study participation (per 45 CFR 46.111(a) (3)). Include information about approximately how many DUHS subjects will be recruited. If subjects are to be compensated, provide specific prorated amounts to be provided for expenses such as travel and/or lost wages, and/or for inducement to participate.

To screen for eligible patients, a request for Waiver or Alteration of Consent and HIPAA Authorization will be obtained prior to start of study. An advertisement flyer and advertisement will be used. MyChart messages to subjects will be used, facilitated by DOCR. We gather screening information by reviewing MD appointments, medical history and clinical diagnosis from Epic Maestro Care, from Duke clinician referrals, and/or utilizing the phone script.

Patient's research opt-out status will be noted prior to approach. If patient expresses the would like to opt-out of all research contact, the PI or designee will complete the REDCap Survey (<https://redcap.duke.edu/redcap/surveys/?s=9NX7DY7DXX>) to convey the patient's information to the appropriate Maestro Care Analyst team and refer the patient to the Notice of Privacy Practices (<https://www.dukehealth.org/privacy>).

If the opt-out status is not present and the subject expresses interest in learning more about the study, the PI or designee will commence in approaching subject.

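### The ban on aspirin during the study makes no exception for aspirin a doctor has advised for the heart or to prevent stroke or clots, and patients with older vascular events can enrol

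*Combined protocol and SAP*

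**What the plan says.** All references are to the combined protocol and SAP.

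- **The rule.** Study Drug Application at Home introduces its list with "Subjects will be instructed to observe the following instructions". Item 7 reads "Do not take other NSAID (like aspirin, ibuprofen, naproxen, ketorolac, diclofenac, etc.) while enrolled on this study". Its second sentence is "Please contact the study doctor or research staff if you are unsure". Neither sentence mentions dose or the reason for taking aspirin.
- **The diary.** Subjects record study drug use, pain scores and "any other oral pain medication taken". Acetaminophen is the permitted rescue medicine.
- **Who is kept out.** Exclusion 11 reads "Subjects who, within the past 3 months, have history of heart attack, stroke, or blood clot". Exclusion 12 reads "Recent coronary artery bypass graft surgery (CABG) (i.e., within 6 months of screening". Exclusion 14 lets the investigator exclude a subject for severe liver or kidney disease or for "any other medical condition within 3 months of screening that may interfere with" participation.
- **Who can come in.** The age range is 18 to 80. Inclusion 5 admits patients who take an NSAID for their musculoskeletal pain if that pain is inadequately controlled. It is silent on aspirin taken for any other purpose.
- **Screening.** Subject Recruitment and Compensation describes "reviewing MD appointments, medical history and clinical diagnosis from Epic Maestro Care", and Baseline Assessments lists a medical history review before dosing.
- **Follow-up.** The visit is one week after first dosing, give or take a day. A remote visit is allowed, with a physical visit to follow when the subject is able.

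**The concern.** Aspirin is not only a painkiller. Some people who have had a heart attack, stroke, clot or bypass operation take it on medical advice to prevent another event. Instruction 7 names aspirin first among the barred drugs and does not separate that use from use for pain. The two vascular exclusions are time-limited, so they do not remove the people most likely to be taking it.

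The issue is patient safety, not inference. A subject who does what the instruction says could interrupt a preventive medicine because of the trial, with no clinician having decided that this is acceptable. The interruption could also go unseen. The diary asks about pain medicines taken, not other medicines stopped, and no contact is scheduled between dispensing and the one-week visit.

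The plan gives no reason for the NSAID ban, although the template text under Design & Procedures asks authors to cover therapies stopped for the protocol. Two reasons are plausible: a clean analgesic background, or avoiding NSAID harm on top of topical diclofenac. Neither requires a subject to stop this aspirin unadvised. Under the first, the aspirin can continue with the investigator's agreement. Under the second, the patient should not be enrolled.

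**Working it through.** The plan gives no figure for aspirin use, so there is none to reproduce. The check compares the provisions and then does two short calculations.

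**1. Could an aspirin user with an older event pass through?** Take a patient whose heart attack was more than 3 months ago, or whose bypass surgery was more than 6 months ago, and who takes aspirin on a doctor's advice.

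- *Exclusions 11 and 12:* not triggered, because the event is outside the window.
- *Exclusion 14:* may be triggered, but it is discretionary. It depends on a condition within 3 months of screening that may interfere with participation. A stable, older event need not meet that.
- *Exclusion 5 (uncontrolled reflux or past peptic ulcer):* removes some aspirin users for another reason, but not this patient as such.
- *Record and history review:* may reveal the event. No visible text tells staff to ask about aspirin or what to do if it is found.
- *Instruction 7, first sentence:* applies, and names the drug.
- *Instruction 7, second sentence:* helps a subject who is unsure. A subject who sees aspirin listed has less reason to be unsure.

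Each safeguard may work, but none is certain to.

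**2. How long could the gap last?** Input: visit at 7 days ± 1 day (Follow-Up).

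- Shortest: 7 − 1 = 6 days.
- Longest: 7 + 1 = 8 days.

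This assumes the subject follows the ban from first dose to the visit. Dropout shortens it. If being enrolled runs on to the physical visit required after a remote one, it could exceed 8 days; the plan sets no date for that visit.

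**3. How many people?** Inputs: 76 per group and 240 to be consented (Power Calculation). Target completers: 2 × 76 = 152. Let *p* be the share of subjects taking such aspirin and *q* the share of those who would stop. Neither is in the documents.

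- Possible users = N × *p*. For each 1%: 152 × 0.01 = 1.52, and 240 × 0.01 = 2.4.
- Subjects who stop = N × *p* × *q*. With *q* anywhere from 0 to 1, each 1% of users gives 0 to 1.52 among 152, or 0 to 2.4 among 240.
- Users in the diclofenac arm if all enrol and continue, at 1:1 allocation: 76 × 0.01 = 0.76 per 1%, or 120 × 0.01 = 1.2 if all 240 consented subjects are randomised.

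The 152 is the firmer base, since not everyone consented need be dosed.

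**The case against.** The best case for the plan has four parts.

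*Context narrows the rule.* Instruction 7 comes shortly after the acetaminophen allowance and a diary entry about pain medicines, and it lists aspirin among analgesics. A subject could fairly read it as covering pain use only. That reading is open, but the text does not say so. Inclusion 5 shows that the authors state the indication when they mean to limit by it.

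*Clinicians are already involved.* Records and history are reviewed, exclusion 14 is available, instructions are given in clinic, and unsure subjects are told to call. Under Data & Safety Monitoring, adverse events go to the principal investigator immediately and are reviewed weekly. This lowers the chance of an unadvised stop and stands as mitigation. None of these steps mentions aspirin, however, and adverse event review would not detect a stop that caused no event.

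*The deciding papers are not in the file.* Subjects receive separate written instructions and a consent form. This stands in full: an exception may exist there. If it does, instruction 7 should be brought into line with it.

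*The size is unknown.* This also stands. The documents give no prevalence of such aspirin use and no risk for a one-week pause.

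A reader might infer more than the documents support: that the trial will take a known number of patients off heart medicine, that patients would be harmed, or that the plan has no protection at all. The documents give no count, show no harm, and contain discretionary safeguards that could work.

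**Conclusion.** The point holds as a safety gap in the wording. Instruction 7 bars aspirin for everyone with no exception for doctor-advised preventive use, while exclusions 11 and 12 leave patients with older vascular events eligible. Followed literally, the rule could lead such a subject to stop that aspirin for about one week without a clinician's decision.

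The 6 to 8 days depends on full adherence and no later physical visit. The number affected cannot be stated beyond about 1.5 of 152 completers for each 1% who take such aspirin, and that counts possible users, not people shown to stop. That some eligible patients take aspirin for this purpose is an assumption. Confidence is medium, because the number affected is unknown and the handout and consent form could not be checked.

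A reader might also conclude that the whole ban should cover only NSAIDs taken for pain. That goes too far: it would allow ibuprofen or naproxen taken for other reasons, such as fever, and nothing in the plan calls for that. The gap concerns doctor-advised aspirin only. No effect on bias, power or the non-inferiority conclusion is claimed.

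**What to change.** Keep the ban on all other NSAIDs as written and add one narrow exception to instruction 7:

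> *If a doctor has told you to take aspirin for your heart or to prevent stroke or clots, do not stop it; tell the study staff.*

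Ask about such aspirin at the existing baseline history, and complete that item before randomisation. The investigator then decides, also before randomisation, whether the subject enrols while continuing the aspirin or is not enrolled. Check that the handout and consent form say the same.

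The cost is one sentence, one baseline question and one recorded decision, with no added visit and no change in sample size. The downside is some aspirin use in both arms, including alongside topical diclofenac. If the sponsor finds that combination unacceptable, it should not enrol these patients rather than have them stop, which would mean one added eligibility criterion.
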